6.3.3 Recommendations and restrictions

Subjects will be asked to comply with the following study recommendations:

Report any adverse events to the investigator,

Do not take any new medication without informing the investigator, even paracetamol

No sunlight or UV light on the face for the duration of the study,

No make-up on the face for 12 hours prior to the peel and assessment visits

No make-up on the face during the 12 hours prior to the peeling and evaluation visits,

In case of non-compliance with these recommendations, the investigator should report the in Deviation log or if necessary contact the sponsor

If these recommendations are not followed, the investigator can decide on the subject's withdrawal or should contact the sponsor to discuss the withdrawal of the subject if necessary,

6.3.4 Criteria and procedures for subject withdrawal or lost to follow-up

6.3.4.1 Criteria and modalities for drop out subjects

Subjects will be free to withdraw from the study at any time if they wish so and for any reason, without having to provide any justification to the investigator.

The investigator has the right to withdraw a subject for any reason, for its best interests, including illness or an adverse event.

The sponsor may decide to withdraw subjects for major deviation to the protocol, for administrative reasons or for any other valuable reason ethically justified.

Subjects may discontinue their participation in the study for the following reasons:

1. *Eligibility: Inclusion/Exclusion criteria*
2. *Adverse event:* the investigator has the right to withdraw a subject in case of intercurrent illness or adverse events or if in the investigator's opinion, continuation in the study would be detrimental to its well-being.
3. *Consent withdrawal:* subject have the right to withdraw his consent at any time and for any motive, without their right to treatment being affected.
4. *Untraceable subject* if a subject does not come to the scheduled visits, several attempts have to be done to try to contact him/her; to obtain the reasons for non-attendance.
5. *Protocol non-adherence:* the investigator has the right to withdraw a subject in case the subject does not respect the study procedures and/or restrictions.

6. Other: administrative or personal reasons for instance

6.3.4.2 Modalities of recording data for drop out subjects

In all cases, the reason for withdrawal must be recorded in the eCRF and the source document and should include any available and appropriate complementary information.

The investigator must make every effort to contact subjects who dropped-out of the study early. In the case where no visit is possible a registered letter with acknowledgement of receipt may be sent to the subject. All the documentation concerning that subject must be as complete as possible.

6.3.4.3 Modalities for the follow-up of drop out subjects

At the study end visit, the investigator will check subject's health and if there is no reason for additional follow-up, he will complete study end form accordingly.

In the case of early study termination, the investigator must make every effort to contact the subject. The subject must be followed up to state the reason for withdrawal and to establish whether the reason is an adverse event. Since the moment the investigator knows the early termination or exclusion, the withdrawal of the subject must be if possible formalized by a visit. If possible, all examinations scheduled for the final study day must be performed on all subjects who received the investigational device but do not complete the study according to the protocol.

When the premature exit is due to an adverse device effect or an adverse event linked to the CIP procedures, the subject must be followed by the investigator until the resolution or the stabilization of the symptoms.

6.3.5 Enrolment procedure

Subjects will be pre-selected by phone from Eurofins Dermscan Pharmascan data base, according to inclusion and exclusion study criteria. This data base is constituted from registration files of people wishing to participate in clinical studies at Eurofins Dermscan Pharmascan.

Advertisement will be placed in Eurofins Dermscan Pharmascan website.

Pre-selected subjects will come to the site for consent form signature on D0 visit and then will be included if eligible according to inclusion and exclusion criteria. The informed consent process is explained in section 13.

6.3.6 Randomization procedure

None.

6.3.7 Duration of the clinical investigation

Clinical investigation beginning: Q4 2022

Clinical investigation end: Q1 2023

Clinical investigation global duration: 17 weeks

Duration by subject: 78 days

6.3.8 Sample size

33 subjects will be included in total on Sponsor's request.

6.3.9 Enrolment period

The enrolment period will last approximately 6 weeks to include the 30 subjects.

6.3.10 Relationship of investigation population to target population

The investigation population and the target population are the same.

6.3.11 Information on vulnerable population

Not applicable.

6.3.12 Subjects' identification

Each subject having signed a consent form will be assigned a “screening subject number” according to his/her chronological order of arrival in the study, from 501, preceding by the letter “S” (i.e. S501).

Then, each subject included will be assigned a “subject number” identifying him/her according to his/her chronological order of selection in the study and from 01.

In addition, each subject will be identified with the first letter of name and first letter of first name.

6.3.13 Financial compensation

A **compensation of 300 PLN** for the constraints suffered and the incurred travel expenses will be paid following the end of subject's participation in the study, if the missing elements (product(s), questionnaire(s), daily-log etc.) are brought back and if all the visits, acts and measurements were made. In case of subject's withdrawal from the study, failure to follow instructions given in the information sheet or in case of premature study end for sanitary or administrative reason, the compensation will be paid proportionally to the duration of subject's participation in the study, to acts made (linked to the investigational device) and associated constraints and to the number of available evaluations.

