Exclusion criteria:	
1. Pregnant or nursing woman or planning a pregnancy during the study.2. Subject who had been deprived of their freedom by administrative or legal decision or who is under guardianship.3. Subject in a social or sanitary establishment.4. Subject participating to another clinical research or being in an exclusion period for a previous study.5. Intensive exposure to sunlight or UV-rays within the previous 3 months and foreseen during the study.6. Subject with any skin or systemic disease (acute and/or chronic), in the previous year, likely to interfere with the measured parameters or to put the subject to an undue risk.7. Subject having history of allergy or hypersensitivity to one of the components of the tested device.8. Subject receiving any treatment that, in the opinion of the clinical investigator, may interfere with test results or put the subject to undue risk.9. Subjects on topical or oral treatments (such as Benzoyl Peroxide, Retinoic Acid, Isotretinoine) that did not stop the treatment 30 days before their first peel (risk of over-peeling).10. Subjects with known salicylism or related medical indications.

DERMOSCIENCES FRANCE	Medical Device CIP # 22E2387	Final version 1.0 Date: 16.08.2022	Confidential Page 12/49
-------------------------	---------------------------------	---------------------------------------	----------------------------

Investigational device: Name / code Galenic form Dosage and duration	CRYSTAL PEEL Liquid 3 applications performed by the dermatologist: 2.5 ml of Crystal Peel applied with a cotton swab on the face. Apply up to 3 coats, waiting 1 minute between each coat. Leave the last coat on for up to 5 minutes, while observing the skin's reaction.
Administration route	Topical administration
Endpoints:	
Primary endpoint: Comparison of the change from baseline of total sum of lesions on each visit.
 
Secondary endpoints: Pores and texture analysis Visual effect - photographs Investigator Global Assessment score Patient Global Assessment score Local and overall tolerance of the Crystal Peel Subject's self-evaluation on D78 using a questionnaire. Adverse events number

Study Procedures:	D0, D15 (peeling act), D36 (peeling act), D57 (peeling act), D78

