6.4.1.2 Study schedule

Visit 1: D0

- Subjects will come to the investigational site with their completed diary.
- Information of the subjects on study aims and schedule.
- Signature of consent form in two copies by the subject and the investigator in charge of the screening visit.
- Medical examination for verification of subject's health state, collection of previous medical history, previous and actual treatments.
- A urinary pregnancy test will be performed for women with childbearing potential.
- Checking of inclusion and exclusion criteria.
- Distribution to the subjects of accompany treatment with the instructions of use.
- Colorface standardized photos will be taken by the Technician.
- Acne lesions will be counted by the Investigator.
- Distribution of the ID card and diary so they can note the adverse events and concomitant treatments / acts.

Visit 2, 3 and 4: D15, D36 and D57

- Subjects will come to the investigational site with their completed diary.
- Checking of exclusion criteria.
- Colorface standardized photos will be taken by the Technician.
- Acne lesions will be counted by the Investigator.
- Peeling act will be performed by the Investigator.
- Record of AE and concomitant treatments.

Visit 5: D78

- Subjects will come to the investigational site with their completed diary.
- Checking of exclusion criteria.
- Colorface standardized photos will be taken by the Technician.
- Acne lesions will be counted by the Investigator.
- Subjective questionnaire.
- Scoring of Patient global assessment.
- Score of Investigator global assessment.
- Record of AE and concomitant treatments.

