10.1 PROCEDURES FOR EVALUATING SUBJECT COMPLIANCE

The devices will not be handled by subjects.

At each visit, subjects will be questioned concerning the use of any topical or systemic prescription or other products. Subjects will also be questioned about prohibited activities such as sun exposure.

The investigator will instruct the subject of the importance of adhering to the protocol. If it can be proven that the subject is obviously not compliant, the investigator can decide to withdraw him from the study.

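### Section 6.3.13 has no adverse-reaction exception: a subject who misses a peel or is withdrawn because of a reaction forfeits full pay, which is a reason to tolerate or not report it

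*Combined protocol and SAP*

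**What the plan says.** Section 6.3.13 offers a "compensation of 300 PLN" as a single sum for the burden of taking part and for travel. It is due in full when outstanding items are handed back and "if all the visits, acts and measurements were made".

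Three events move the subject to reduced pay:
- withdrawal ("In case of subject's withdrawal from the study", with no reason distinguished);
- "failure to follow instructions given in the information sheet";
- early end of the study for sanitary or administrative reasons.

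Reduced pay depends on time in the study and is also proportional "to acts made (linked to the investigational device) and associated constraints and to the number of available evaluations". No weights are given, and adverse reactions are not mentioned.

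The synopsis fixes the number of visits and peels: "D0, D15 (peeling act), D36 (peeling act), D57 (peeling act), D78".

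Other sections foresee that a reaction may end treatment. Section 6.2.3.2 allows the investigator to interrupt the device for an adverse device effect, and section 6.3.4.1 lists adverse events as a reason for withdrawal. For reporting, section 6.3.3 asks subjects to tell the investigator of any adverse event, and the Visit 1 list in section 6.4.1.2 includes "Distribution of the ID card and diary so they can note the adverse events and concomitant treatments / acts".

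**The concern.** Section 4.2 says that reactions may be immediate or delayed, and the visits from D15 onward are 21 days apart. A delayed reaction that settles before the next visit reaches the record mainly if the subject writes it down or mentions it. Mentioning it may lead the investigator to withhold the next peel or withdraw the subject, and section 6.3.13 then removes the entitlement to full pay. A subject who understands the rule gains by staying silent or by putting up with the reaction.

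Two things are at stake. One is the completeness of the tolerance and adverse-event data, which are secondary endpoints. The other is the welfare of a subject who might accept a further peel that an honest report would have led the investigator to reconsider.

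**Working it through.** The plan has no figure of its own to reproduce here: it states a maximum and three scaling factors, without weights. The check asks what the text would pay in plausible situations.

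**Inputs**
- Full pay: 300 PLN (section 6.3.13).
- Duration: 78 days per subject (section 6.3.7).
- Peels: 3; visits: 5 (synopsis).
- Planned subjects: 33 (section 6.3.8).
- Assumptions: the device-linked acts are the peels, and each visit counts as one evaluation.

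**Formulas**
- Duration alone: 300 x days/78.
- Acts alone: 300 x peels/3.
- Evaluations alone: 300 x visits/5.
- Because the weights are unknown, the equal-weight mean and the product of the three fractions are also shown.

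For withdrawal at D15 after peel 1: 300 x 15/78 = 57.7; 300 x 1/3 = 100; 300 x 2/5 = 120; mean (57.7 + 100 + 120)/3 = 92.6; product 300 x 0.192 x 0.333 x 0.4 = 7.7.

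| Situation (PLN) | Duration | Acts | Evaluations | Mean | Product |
|---|---|---|---|---|---|
| Withdrawn D15, after peel 1 | 58 | 100 | 120 | 93 | 8 |
| Withdrawn D36, before peel 2 | 138 | 100 | 180 | 139 | 28 |
| Withdrawn D57, before peel 3 | 219 | 200 | 240 | 220 | 117 |
| Stays to D78, peel 3 not given | 300 | 200 | 300 | 267 | 200 |
| All 3 peels and 5 visits done | 300 | 300 | 300 | 300 | 300 |

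**Reading the table**
- Withdrawal costs between 300 - 240 = 60 PLN (D57, evaluations alone) and 300 - 58 = 242 PLN (D15, duration alone) on any single factor.
- The fourth row is conditional. A subject who stays but is not given a peel fails the full-pay condition, yet fits none of the listed triggers unless an instruction was broken. The text does not say what that subject is paid.
- Deleting the acts factor would not by itself protect a subject withdrawn early. At D15 the mean of the two remaining factors is (57.7 + 120)/2 = 88.8 PLN, against 92.6 with three. A rule based on visits alone would pay 2/5 x 300 = 120 PLN. Only an explicit exception restores 300 PLN.

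**The case against.** The strongest reply is that pro-rating by burden is coherent. The sum compensates for constraints and travel, and someone who has fewer peels and visits bears less of both. Peels are one of three unweighted factors, and 300/5 = 60 PLN per visit, travel included, is modest. Nothing in the documents shows that it changes what subjects report. Reactions also have other routes into the record: the practitioner watches the skin during application (section 6.2.1.2), local tolerance is on the flow chart from V2 to V5 (section 6.1.4), and the investigator records observed signs at each visit (section 14.3.1).

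Most of this stands. It limits the point to reactions arising between visits and leaves the size of any effect unknown. It does not explain why a subject stopped because of a reaction is paid on the same terms as one who simply leaves.

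A reader might infer more than the text supports:
- **Pay is cut simply in proportion to peels missed.** It is not. Duration and evaluations also count, and no weights are given.
- **Rinsing off one application early lowers pay.** Section 6.2.1.2 provides for immediate removal, and nothing says that a shortened application is not an act made.
- **Admitting a prohibited product lowers pay.** Section 10.1 says "subjects will be questioned concerning the use of any topical or systemic prescription or other products", so such use is learned largely by self-report. But the reduced terms apply only if an information-sheet instruction was broken, and that sheet is not among the documents reviewed. Even then, a subject with three peels, five evaluations and 78 days scores 100% on every factor and receives 300 PLN. A loss needs a further step, such as withdrawal, which is discretionary.
- **The rule biases the lesion count.** Under section 7.1 an included subject with a post-baseline value is in the ITT set, so a product user would normally contribute whether or not the use is disclosed. Any shift comes from the product use, not from the pay rule. Where ITT and PP differ by less than 10%, only ITT is analysed; one subject in 30 is 3.3%.

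**Conclusion.** The point holds in a limited form. Full pay requires all acts, pay after withdrawal depends partly on peels received, and there is no exception for a peel missed or a withdrawal caused by a reaction. That gives subjects a financial reason to tolerate or not report between-visit reactions.

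The individual loss on withdrawal is 60 to 242 PLN out of 300 when each factor is taken alone, on the assumptions stated with the table. The true amount depends on weights that the plan does not give. How many reactions would go unreported cannot be estimated from the documents, and no distortion of the primary endpoint is shown. This is a minor drafting point about safety reporting and subject protection, worth correcting because the correction is simple and cheap.

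**What to change.** In section 6.3.13 and the information sheet:
1. Remove device-linked acts as a scaling factor, and remove acts as a condition for full pay.
2. State that payment is not reduced by reporting an adverse event, or when a peel is interrupted, not given or followed by withdrawal because of an adverse reaction.
3. Keep proportional pay, by duration and evaluations, for other withdrawals.

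The second step does the main work, since the first alone leaves a subject withdrawn at D15 with about 89 PLN on equal weights. Whether non-adherence should remain a trigger for reduced pay is a separate trade-off and is not part of this change.

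The cost is a wording change to two documents. Total payments cannot exceed 33 x 300 = 9,900 PLN. As an illustration, if the 33 - 30 = 3 subjects allowed for as losses all left at D15 because of a reaction, the extra payment would be 3 x (300 - 120) = 540 to 3 x (300 - 58) = 726 PLN on the single-factor figures. The downside is that a few subjects who stop because of a reaction are paid in full, as is anyone who misses a peel for another reason but attends every visit. Someone could also claim a reaction in order to leave with full pay; the reason for withdrawal, which section 6.3.4.2 already requires to be recorded, gives a check on that. The incentive to attend visits is kept.

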6.3.14 ID card

Each subject receives, from the investigational site, a personal identification card to be kept for the duration of the study. The card will specify: subject name and number, sponsor name, study reference, beginning date and scheduled study end, investigation site address with the name and phone number of the investigator and the urgent phone number.

6.4 PROCEDURES

6.4.1 Description of all the clinical investigation-related procedures that subjects undergo during the clinical investigation

6.4.1.1 Staff involved in the study

There will be three different kinds of personnel involved in the study:

- Investigators performing the peeling act (qualified practitioners): they will oversee the inclusions of subjects and they will be in charge of the device application;
- Live independent evaluators (investigators): the follow-up of subject's and the scoring in live.
- Technicians: operators: they will oversee the photographs taking .

6.4.1.2 Study schedule

Visit 1: D0

- Subjects will come to the investigational site with their completed diary.
- Information of the subjects on study aims and schedule.
- Signature of consent form in two copies by the subject and the investigator in charge of the screening visit.
- Medical examination for verification of subject's health state, collection of previous medical history, previous and actual treatments.
- A urinary pregnancy test will be performed for women with childbearing potential.
- Checking of inclusion and exclusion criteria.
- Distribution to the subjects of accompany treatment with the instructions of use.
- Colorface standardized photos will be taken by the Technician.
- Acne lesions will be counted by the Investigator.
- Distribution of the ID card and diary so they can note the adverse events and concomitant treatments / acts.

Visit 2, 3 and 4: D15, D36 and D57

- Subjects will come to the investigational site with their completed diary.
- Checking of exclusion criteria.
- Colorface standardized photos will be taken by the Technician.
- Acne lesions will be counted by the Investigator.
- Peeling act will be performed by the Investigator.
- Record of AE and concomitant treatments.

Visit 5: D78

- Subjects will come to the investigational site with their completed diary.
- Checking of exclusion criteria.
- Colorface standardized photos will be taken by the Technician.
- Acne lesions will be counted by the Investigator.
- Subjective questionnaire.
- Scoring of Patient global assessment.
- Score of Investigator global assessment.
- Record of AE and concomitant treatments.

6.4.2 Description of effectiveness parameters

6.4.2.1 Counting of the acne lesions

Investigator will perform acne lesions counting (front, 2 cheeks, the chin above the jaw line (excluding the nose)) using both visual observation and palpation on each visit (baseline, D15, D36, D57 and D78). Total lesions will be defined as the sum of inflammatory lesions (papules, pustules), non-inflammatory lesions (whiteheads and blackheads) and other acne lesions (nodules).

The change of the number of acne lesions from baseline will be calculated on each visit.

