6.1.4 Method and timing for assessing, recording, and analysing variables

Procedure (time-points)	V1	V2	V3	V4	V5
Intervals	D0	D15 (+/-1)	D36 (+/-2)	D57 (+/-2)	D78 (+/-3)
Checking the inclusion/non-inclusion inclusion/non-inclusion criteria	●				
Physical examination/Vital signs / medical history and treatment	●				
Informed Consent Form	●				
Pregnancy test	●				
Exclusion criteria	●	●	●	●	●
Use of associated treatment		●			
PEELING ACT					
Colorface Standardized Photos (X3)	●	●	●	●	●
Lesions counting	●	●	●	●	●
pores analysis by Newtone	●	●	●	●	●
texture analysis by Newtone	●	●	●	●	●
Local tolerance		●	●	●	●

Procedure (time-points)	V1	V2	V3	V4	V5
Intervals	D0	D15 (+/-1)	D36 (+/-2)	D57 (+/-2)	D78 (+/-3)
Dispense cosmetic products and daily log	●				
Collect daily log		●	●	●	●
Subjective evaluation questionnaire					●
IGA					●
PGA					●
Adherence control, record of AE, concomitant treatments	●	●	●	●	●
End of study form					●

6.1.5 Equipment to be used for assessing, recording and analysing variables and arrangements for monitoring maintenance and calibration

The device used for the photographs taking will be the Colorface®. The maintenance of device used for the clinical investigation were checked before study beginning. The calibration of these devices (by the technician) is done regularly.

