6.2.1.3 Precautions for use

For external use only and for use on a limited area, due to the presence of Salicylic Acid. For adults only.

- Skin preparation is recommended 15 days before the first peel.
- Must only be used by trained healthcare professionals. Required knowledge of complications associated with the application of medical devices and how to react is necessary.
- Always use protective gloves during the procedure and clean the glass cup carefully between each peel session. Cotton buds should be disposed of after each use.
- Do not use alcohol or acetone-based cleanser.
- Avoid the lip area and nasolabial folds. Do not swallow.
- Avoid eyes and mucous membranes: in the event of accidental contact, rinse thoroughly with water, and use a saline solution.
- Avoid sun exposure and use sun protection (K Ceutic or Sun Ceutic 50+) for 4 weeks after the treatment and in-between treatments.
- Keep out of the reach of children.
- In case of alteration in the product's appearance, do not use the medical device.
- Protocol variations should be based on assessment of patient skin type, treatment tolerance and desired results.
- Do not apply on a large area or other areas of the body to avoid a high absorption of Salicylic Acid.
- Never hold the medical device above the patient to avoid accidental spillage.
- If an allergic reaction is considered likely, apply the product to a 1 cm² sized area behind the ear, following the exact same protocol. If no unusual reaction is observed within 72 hours, the facial peel can go ahead.

The practitioners are asked to refer to the last version available of IFU/IB.

6.2.2 List of other medical device or medication to be used during the clinical investigation

No other medical device or medication is planned to be used according to the CIP. However the associated cosmetic products are to be used during the investigation.

Accompanying products are commercially available products developed by DERMOSCIENCES LTD. They are used to prepare and protect the skin during the peeling procedures and to maintain the effect of the peeling.

Foamer 15 (15 % glycolic acid foamer):

- Use as a pre-peel: Cleanse the face with 4 squeezes spread over the whole face, rinse thoroughly after 2 minutes or as soon as the first tingling appears and dry.
- Use at home: Apply a small amount of foam to the clean and dry face.

Massage and rinse with water after two minutes or as soon as you start to feel tingling.

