7.2.1 Primary endpoint

Comparison of the change from baseline of total sum of lesions on each visit- objective counting of the lesions by the investigator.

Total lesions will be defined as the sum of inflammatory lesions (papules, pustules), non-inflammatory lesions (whiteheads and blackheads) and other acne lesions (nodules).

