7.2.2 Secondary endpoint(s)

- Pores and texture analysis (will be performed by Newtone with Colorface acquisitions)
- Visual effect (Standardized anonymized photographs (face, 45° at left, 45° right) with Colorface)
- Investigator Global Assessment
- Patient Global Assessment
- Local and overall tolerance of the Crystal Peel, a salicylic acid-based peel, used under the normal conditions of use recommended by the manufacturer.
- Subject's self-evaluation on D78 using a questionnaire.
- Potential adverse events collection.

Analysis of primary and secondary endpoints 'parameters':

For each continuous variable obtained from devices: A mixed linear model for repeated measurements (PROC MIXED) will be fitted to raw data.

Using the adjusted means obtained from this model (LS-Means), the contrast of interest will be built:

- To assess the change from first measurement at each time

The underlying assumptions (normality and homoscedasticity of residuals) will be checked using Shapiro-Wilk test ($\alpha=0.01$) and graphical representations.

In case of strong deviation, a transformation of the data or a non-parametric approach (Wilcoxon signed rank tests) will be performed.

The raw score will be summarized using descriptive statistics for quantitative data by time point. A Wilcoxon signed rank test will be applied to test whether the change from baseline is statistically significant.

The categorical data will be summarized in frequency (N) and percentage (%) associated with its 95% confidence interval by time point.

The questionnaire will be summarized in frequency (N) and percentage (%).

The adverse events will be analysed.

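### Every planned contrast starts at D0, 15 days before the first peel, and none separates this device-free lead-in from the period with peels

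*Combined protocol and SAP*

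**What the plan says.** **Reference visit.** Section 7.2.1 defines the primary endpoint as "Comparison of the change from baseline of total sum of lesions on each visit". Section 6.4.2.1 lists baseline separately from D15, D36, D57 and D78 and adds: "The change of the number of acne lesions from baseline will be calculated on each visit". Section 6.4.2.2 likewise treats D15 as a time point after baseline. Baseline is therefore D0. For variables obtained from devices (pores and texture), the only model contrast in section 7.2.2 is "To assess the change from first measurement at each time". The Wilcoxon test in that section also uses change from baseline. It is not entirely clear which of the two methods applies to lesion counts, but both refer to D0.

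**Peels.** The synopsis gives the visits as "D0, D15 (peeling act), D36 (peeling act), D57 (peeling act), D78". In the visit list of section 6.4.1.2 the count at D15, D36 and D57 comes before the peel. Only section 6.4.2.2, on photographs, says outright that the assessment precedes application.

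**Cosmetics.** The D0 visit includes "Distribution to the subjects of accompany treatment with the instructions of use". Section 6.2.2 says of these products: "They are used to prepare and protect the skin during the peeling procedures and to maintain the effect of the peeling". They include a 15% glycolic acid foamer with a home direction, "Use at home: Apply a small amount of foam to the clean and dry face", and a night cream whose precaution implies a retinol base. Section 6.2.1.3 recommends skin preparation 15 days before the first peel. The flow-chart in section 6.1.4 has a row "Use of associated treatment" with a single mark, which appears under the second visit (D15).

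**Attribution.** The hypothesis in section 5.4 names Crystal Peel. Sections 2.5 and 5.1 tie the claims to use according to the instructions. Section 6.4.5 names no factor that could affect interpretation, and section 7.8 identifies no confounder.

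**The concern.** In a single-arm, open study the whole inference rests on the choice of starting point. Three things unrelated to any peel can lower the count between D0 and D15: the cosmetics, if home use begins at D0; regression to the mean, because subjects must have at least 6 inflammatory and 12 non-inflammatory lesions to enter; and natural course. Whatever persists is contained in the D36, D57 and D78 results and would be read as an effect of the device.

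The plan does not identify D15-D0 as a comparison without device exposure, and it offers no comparison that begins just before the first peel. If that comparison is chosen only after the data are seen, it will be post hoc.

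**Working it through.** **Figures in the plan.** Section 6.1.6 gives 33 included for 30 evaluable (an allowance of 1 - 30/33 = 9.1%). Tests are two-sided at 5% (section 7.3). No effect size, SD, expected lesion count or power is stated, so every size below rests on assumptions.

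**Time without the device.** The 15 days before the first peel are 15/36 = 42%, 15/57 = 26% and 15/78 = 19% of the D36, D57 and D78 intervals. With the visit windows the last figure runs from 14/81 = 17% to 16/75 = 21%. These are shares of days, not of effect. One of the four contrasts from D0 (D15-D0) has no peel in it.

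**Persisting lead-in fall, no peel effect.** Let δ be the fall from D0 to D15 in units of the SD of change, and let it stay constant to D78. For a paired t-test with n = 30, the chance of a significant improvement is P = 1 - F(t; 29, δ√30), where F is the noncentral t distribution function and t is the 97.5% point of t with 29 degrees of freedom.

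| δ | δ√30 | n = 30 | n = 27 | n = 33 |
|---|---|---|---|---|
| 0.1 | 0.55 | 7.6% | 7.2% | 8.0% |
| 0.2 | 1.10 | 18.4% | 16.9% | 19.9% |
| 0.3 | 1.64 | 35.5% | 32.3% | 38.7% |
| 0.5 | 2.74 | 75.4% | 70.6% | 79.5% |

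The Wilcoxon test, simulated with normal changes and n = 30, gives 17.4%, 33.7% and 73.0% at 0.2, 0.3 and 0.5 SD. For D78-D15 the lead-in fall cancels. Simulated two-sided rejection rates are 5.1%, 4.9% and 4.8% at shifts of 0.2, 0.5 and 0.8 SD, that is, about 2.5% in the direction of improvement.

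**Count model.** Gamma-Poisson counts, selected at D0 on the 6/12 threshold, with assumed between-subject CV 0.6, visit-to-visit CV 0.15 to 0.35, and assumed source means (inflammatory/non-inflammatory). Rates are for a significant improvement.

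- Regression to the mean alone, D78-D0: 18-26% at means 8/18, 6-8% at 14/28, about 4% at 20/40, about 3% at 30/60. It matters mainly if typical counts lie near the threshold.
- Constant 10% lead-in fall (means 8/18 to 20/40, as in the cases below): D78-D0 32-83%, D78-D15 2-3%.
- Cosmetic effect of 10% at D15 growing to 20% by D78: D78-D0 82-100%, D78-D15 25-66%.
- Temporary 10% rise at D15, gone by D78: D78-D15 18-53%; D78-D0 4-8% (14/28, 20/40) or 18-26% (8/18).
- True 20% peel effect: detected by D78-D15 in about 67-99% of trials (lower end with a constant 10% cosmetic fall added) and by D78-D0 in 82-100%.

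**The case against.** **D0 may be the intended reference.** Section 2.1 describes Crystal Peel as a kit that contains Foamer 15. Sections 2.5 and 5.1 refer to use according to the instructions, and preparation is recommended. On that reading D0 to D78 measures the regimen. This stands for those claims. It goes less far for section 5.4, because the night cream and the moisturiser are not in the kit list and the plan nowhere states a regimen hypothesis.

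**The lead-in is partly visible already.** D15-D0 is a planned contrast and section 7.2 summarises each time point, so a fall would be seen. This also stands. What is missing is its label and a prespecified comparison from D15 with its own uncertainty.

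**Cosmetic use may not start at D0.** Distribution at D0 and the 15-day preparation suggest that it does, but no start date is given and the flow-chart mark may point to D15. The placement is uncertain, since the peeling-act row shows no marks in the text version of the table. If use began at D15, a purely cosmetic 20% fall would pass D78-D15 about as often as a true 20% peel effect. Regression to the mean and natural course would remain in the lead-in either way.

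**Stronger inferences.** A reader might infer that section 5.4 states a peel-only hypothesis which the results cannot support, or that measuring from D15 would isolate the peel. The documents bear out neither. Section 5.4 says only that Crystal Peel is effective, and the cosmetics are also meant to maintain the effect of the peel, in a study without a control arm.

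**Conclusion.** The point holds as a gap in the analysis plan. All lesion-count, pore and texture contrasts run from D0, the first peel is at D15, and nothing planned separates the device-free lead-in from the period with peels, although the conclusion is credited to Crystal Peel and no such factor is acknowledged. This assumes that the D15 count precedes the peel, as the visit list implies.

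The size cannot be known from the documents. If a lead-in fall of 0.1 to 0.5 SD of change persists and the peel does nothing, D78-D0 shows a significant improvement in 8% to 75% of trials instead of 2.5%. If the lead-in change is negligible, so is the bias. The D0 reference is not wrong in itself; it answers the question about the regimen. The D15 reference removes one avoidable component, not all of them. The point should be fixed before analysis, but it does not invalidate the study.

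**What to change.** - State that the lesion count at D15 is made before the peel, and reconcile sections 6.1.4, 6.2.1.3 and 6.4.1.2 on when home use of the cosmetics begins.
- In sections 6.4.2.1 and 7.2, keep D78-D0 as the effect of the whole regimen, prespecify D78-D15 in the same analysis as the change from just before the first peel, and label D15-D0 as a device-free lead-in change. Report the three together for lesion count, pores and texture.
- Word any conclusion from D78-D0 as applying to Crystal Peel together with the accompanying cosmetics, and align sections 2.5, 5.1 and 5.4 and the synopsis.
- Name the cosmetics and the entry threshold in sections 6.4.5 and 7.8.
- State the limits: D78-D15 does not isolate the peel, because cosmetic use continues after D15 (or may begin then) and there is no control arm; and it can overstate benefit if counts rise temporarily in the lead-in.

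**Cost.** Text only, with no new visit, measurement or subject; ethics committee and competent authority review may be needed if the sponsor judges the change substantial (section 9). The reduction measured from D15 may look smaller and is detected somewhat less often: about 67-99% against 82-100% for a true 20% effect under the assumed model.
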